## Comparison of High vs. Standard Dose Flu Vaccine in Pediatric Stem Cell Transplant Recipients

DMID Protocol Number 16-0117

Protocol Version 8.0

Date: 9/12/2019

summary format. The DSMB may be asked to provide recommendations in response to questions posed by the IND sponsor and DMID.

- Ad hoc when a halting rule is met, for immediate concerns regarding observations during this study, or as needed – for a specific safety concern, such as SAE deemed related to the study vaccine.

### j. Halting Rules:

The ISM of each site, DMID, and DSMB will be provided safety data in order to advise on matters of safety, including halting the trial. The safety data will consist of immediate reactogenicity events (in the 15 minutes after vaccination), reactogenicity events recorded on the memory aid (each day for the week after vaccination), AEs, and SAEs. The data will be entered into ONCORE and/or REDCap and provided to the ISM, DMID, and DSMB for review. The presentation of the data will include whether any events contributing towards a halting rule have been met. The frequency of DSMB review will be defined in the charter.

The study will be halted (for further DSMB review/recommendation) if any of the following occur and it was not the result of trauma or accident, scheduled hospitalization or surgery, and is not attributable to disease relapse, GVHD, or and infection due to the immunosuppressed state of the patient. No new subjects will be enrolled if:

1. If one subject has an SAE and the adverse event is deemed severe within 7 days of vaccine that is determined to be related to the study vaccine by the site PI in consultation with the site ISM and the study PI, no new subjects will be enrolled. The SAEs will be reviewed by the DSMB for the relationship with the study vaccine and further discussed with DMID to determine continuation of the study.
2. If four or more subjects have the same Grade 3 event in any reactogenicity category (excluding grade 3 redness/ induration size or grade 3 fever) that is determined to be study vaccine-related, no new subjects will be enrolled. The AEs will be reviewed by the DSMB for the relationship with the study vaccine. For 2019-20, based on safety data from the previous years, the number of subjects will be increased to eight prior to halting.
3. 3 or more subjects have urticaria considered to be study vaccine-related.
4. 1 or more subjects have intramuscular injection-site ulceration, abscess, or necrosis.
5. 1 or more subjects have laryngospasm, bronchospasm or systemic anaphylaxis within 24 hours of administration of study vaccine.
6. 1 or more subjects have acute weakness of limbs or cranial nerve innervated muscles.
7. Any death occurring within the first 7 days following administration of study vaccine.

If any of the halting rules are met, the study will not proceed with the remaining enrollment or vaccinations without a review by and recommendation from the DSMB to proceed. CBER will be notified if a stopping rule has been met at any time during the study. DMID retains the authority to suspend additional enrollment and study interventions/administration of study product during the entire trial, as applicable.

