**f. Serious Adverse Event:**

An SAE is defined as an AE meeting one of the following conditions:

- Results in death during the period of protocol defined surveillance except deaths that are the result of trauma or accident.
- Is life-threatening (defined as a subject at immediate risk of death at the time of the event).
- Requires inpatient hospitalization or prolongation of existing hospitalization during the period of protocol-defined surveillance.
- Results in a persistent or significant disability/incapacity.
- Any other important medical event that may not result in death, be life threatening, or require hospitalization, may be considered an SAE when, based upon appropriate medical judgment, the event may jeopardize the subject and may require medical or surgical intervention to prevent one of the outcomes listed above. Examples of such medical events include allergic bronchospasm requiring intensive treatment in an emergency room or at home, blood dyscrasias or convulsions that do not result in inpatient hospitalization, or the development of drug dependency or drug abuse.

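### The infection exclusion that opens the halting rules (protocol section 16.j) reaches rule 4, so a single injection-site abscess could go uncounted

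*Protocol*

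**What the plan says.** Section 16.j of the protocol opens its list of seven halting rules with a sentence that applies to all of them. A listed event halts the study pending DSMB review only if it did not come from trauma, accident, or planned admission or surgery, and if it "is not attributable to disease relapse, GVHD, or and infection due to the immunosuppressed state of the patient". A short second sentence, "No new subjects will be enrolled if", leads into the numbered list.

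Rule 4 in that list reads "1 or more subjects have intramuscular injection-site ulceration, abscess, or necrosis". It asks for one subject and says nothing about cause. Rule 3, just above it, is worded differently: "3 or more subjects have urticaria considered to be study vaccine-related".

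The paragraph after the list sets the consequence. Once any rule is met, "the study will not proceed with the remaining enrollment or vaccinations without a review by and recommendation from the DSMB to proceed", and "CBER will be notified if a stopping rule has been met at any time during the study". The SAP contains no halting rules and does not bear on the point.

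**The concern.** A one-event trigger with no test of cause sends the first case to the DSMB before anyone at the site has settled why it happened. The opening sentence brings a test of cause back in. For rule 4 that matters because one of the excluded causes, infection arising from immunosuppression, is a ready explanation for an abscess in almost any child in this trial. The text does not say who makes the attribution for rule 4 or on what evidence.

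What is at stake is the automatic step. If the abscess is set aside under the exclusion, the rule has not been met, and the stop to enrolment and vaccination, the DSMB recommendation to proceed and the CBER notice are no longer required. Whether anything happens then depends on someone choosing to act, or on the event being picked up in routine review.

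**Working it through.** No formula applies. The check is to read the opening sentence against each rule and then follow one case through.

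**Which rules test for cause themselves (section 16.j)**

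| Rule | Event | Subjects needed | Own vaccine-relatedness condition |
|---|---|---|---|
| 1 | Severe SAE within 7 days | 1 | Yes; decided by site PI with site ISM and study PI |
| 2 | Same Grade 3 reactogenicity event | 4 (8 for 2019-20) | Yes |
| 3 | Urticaria | 3 | Yes |
| 4 | Injection-site ulceration, abscess or necrosis | 1 | No |
| 5 | Laryngospasm, bronchospasm or anaphylaxis within 24 hours | 1 | No |
| 6 | Acute limb or cranial-nerve weakness | 1 | No |
| 7 | Death within 7 days | 1 | No |

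Three of the seven rules (1 to 3) carry their own condition and four (4 to 7) do not. For rule 4 the opening sentence is therefore the only place in 16.j where an event can be discounted on grounds of cause.

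**Which rule 4 events the infection exclusion touches.** Of the three named, ulceration and necrosis are not infections in themselves. Abscess ordinarily is. So 1 of 3 is affected.

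**One case followed through.** A child develops an abscess at the injection site after a study dose.

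1. Rule 4's threshold is one subject, and there is one. The listed event has occurred.
2. The opening sentence asks whether the event is attributable to infection from the immunosuppressed state. Section C.4 admits only allogeneic HSCT recipients, 3 to 35 months post-transplant at first enrolment, so the explanation is open for essentially every participant.
3. If the answer is no, the rule is met and the consequences in 16.j follow.
4. If the answer is yes, the event does not count and none of them follows automatically.

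**What remains in case 4**

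- Section 16.j sends safety data to several bodies: "The data will be entered into ONCORE and/or REDCap and provided to the ISM, DMID, and DSMB for review". DMID may also suspend at any time, whether or not a rule has been met.
- Section 16.f can make the abscess serious: "Any other important medical event that may not result in death, be life threatening, or require hospitalization, may be considered an SAE when" intervention is needed to avert one of the serious outcomes. The ISM and the DMID Medical Monitor review SAEs in real time (16.i), and the DSMC reviews them quarterly. The note to 16.f, however, removes SAEs attributed to complications of immunosuppressive medication, a closely related attribution.
- Section 16.a limits investigator reporting of non-serious events to Grade 3 with similar exclusions, whereas 16.g requires AEs in the reporting period to be documented whatever their relationship to vaccine.
- The DSMB can meet ad hoc (16.i). The Medical Monitor's stated power to stop covers events that meet the halting criteria, so it inherits the question in step 2.

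These routes are either discretionary or part of routine review. None restores the automatic stop.

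**Exposure under version 8.0.** The version is dated 9/12/2019. Section C.4 places first-time enrolment in 2016-17 to 2018-19, and sections C.1 and C.4 describe 2019-20 participants as repeaters given the same vaccine as the year before. Each is scheduled for two doses.

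**The case against.** The best reply is that a specific term should not be swallowed by a general one. Rule 4 names abscess at the injection site, and every participant is a transplant recipient. If immunosuppression alone were enough to remove an abscess, that word in rule 4 would do almost nothing, so a sensible reader would confine the exclusion to background infection. Section 16.d also says the study product must always be suspect. This is a fair account of what the authors probably intended. It does not settle the matter, because the exclusion is attached to every listed event and nothing in 16.j confines it to background infection or exempts rule 4.

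The exclusions themselves are reasonable. In this population relapse, GVHD and systemic infection would otherwise halt the study for events that have nothing to do with the vaccine. That stands, and nothing here asks for their removal.

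A reader might infer more than the documents support:

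- *That the two opening sentences conflict*, one with exclusions and one without. They are consecutive, the second simply introduces the list, and the closing paragraph of 16.j treats the rules as one set with one consequence. If the second governed alone, the exclusions in the first would do no work.
- *That oversight has a gap.* The ISM, DMID, DSMC and DSMB all remain in place.
- *That the interval between scheduled DSMB or DSMC meetings measures the delay.* It does not, since ad hoc review and DMID suspension are available at any time.
- *That rule 7 has the same fault.* The background-cause exclusions suit deaths in this population, and no defect in that rule is shown.

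**Conclusion.** The point holds as a wording weakness in one safety rule, of low severity. On its ordinary reading, the infection exclusion allows an injection-site abscess to be left uncounted under a rule designed to fire on a single event without regard to cause.

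Its reach is one of three events in one of seven rules, during a season limited to repeaters. It has no bearing on the estimand, the primary analysis or the randomisation. The conclusion rests on two assumptions: that the opening sentence applies to all seven rules, as its wording indicates, and that an abscess would usually be regarded as an infection. The documents give no expected frequency, so no probability of the rule being bypassed is claimed. The DSMB charter, which is not among the documents, might address attribution; if it does, the protocol should say so.

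**What to change.** Add one sentence to section 16.j after the exclusions, for example: *The infection exclusion above does not apply to injection-site events listed in rule 4.* In the same edit, correct the exclusion clause, where two conjunctions stand together before the word infection. The other exclusions stay as they are.

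The cost is this small edit, and an occasional pause in enrolment and vaccination for an abscess that the DSMB later judges unrelated. Version 8.0 already carries a 2019-20 adjustment to rule 2 in the same list, raising its threshold from four subjects to eight, so the clarification would sit naturally beside it.

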**Comparison of High vs. Standard Dose Flu Vaccine in Pediatric Stem Cell Transplant Recipients**

**DMID Protocol Number 16-0117**

**Protocol Version 8.0**

**Date: 9/12/2019**

**Criteria for temporarily delaying vaccine administration:** The following conditions are temporary or self-limiting, and a subject may be included in the study once the condition has resolved, provided that the subject is otherwise eligible: 1). Fever  $\geq 100.4^{\circ}\text{F}/38.0^{\circ}\text{C}$  (oral measurement), or an acute illness within 48 hours of enrollment 2). Receipt of any live vaccines within four weeks or any inactivated vaccines within two weeks prior to potential study vaccination.

Note: if patients were eligible for vaccine 1, they will be eligible to receive vaccine 2 regardless of any changes on their GVHD status, unless it is deemed not medically safe to receive influenza vaccine.

Note: Previous Screen failures who were not vaccinated can be enrolled and will be assigned the same study ID number.

Comparison of High vs. Standard Dose Flu Vaccine in Pediatric Stem Cell Transplant Recipients

DMID Protocol Number 16-0117

Protocol Version 8.0

Date: 9/12/2019

An overview of the study schedule and procedures are described in **Table 3**.

Table 3.	Screening period	Visit 1	Phone / email	Optional Visit	Visit 2	Phone/Email	Optional Visit	Visit 3	Influenza Season	Visit 4 ^	June 30th
Days		0	1-3 and 8-10* days	5-10 days after visit 1	28-42 days	1-3 and 8-10* days after visit 2	5-10 days after visit 2	28-42 days after visit 2		180 ±42 days after visit 2	Day 0 until June 30th
Consent	X	X									
Inclusion/exclusion		X			X						
Physical examination#, oral temperature		X			X						
Peripheral venipuncture or via central line		X		X	X		X	X		X	
HAI, NAI, and microneutralization assay		X**			X**			X**		X	
B/T cell responses		X		X	X		X	X		X	
CBC d/p#		X			X			X		X	
Quantitative CD4, and CD8, CD19#		X			X			X		X	
Quantitative serum IgG, IgM#		X			X			X		X	
Study vaccine administration (HD-TIV or standard dose)		X			X						
Memory aid review			X			X					
Adverse event assessment		X	X	X	X	X	X				
Concomitant medication collection		X	X	X	X	X	X	X			
Immunizations reviewed		X			X			X		X	
Telephone and/or Electronic communication			X			X			Weekly		
Pregnancy Test (if applicable)		X			X						
Collection of Nasal Swab for PCR testing for Influenza***		X^			X^			X^	If symptomatic	X^	X
Proven clinical influenza illness #review		X	X	X	X	X	X	X	X	X	X

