**7. Reporting Adverse Events:**

The investigator is responsible for reporting:

- Any Grade 3 Adverse event that is not attributable to underlying disease for which the transplant was undertaken, **or** not attributable to GVHD, **or** not attributable to complications of immunosuppressive medications that are observed or reported through 7 days following vaccination (Day 0 through Day 7), regardless of their relationship to study product.
- Any other AE will not be reported unless it meets the SAE criteria (see Section 16.f).

Initial vaccine reactions will be assessed for at least 15 minutes after vaccination. Subjects will be asked to record both solicited vaccine reactions and any unsolicited AEs on a memory aid for 7+ days after each vaccination (Day 0 through Day 7). Study personnel will attempt contacting the subjects by telephone and/or electronic communication at 1-3 days and 8-10 days after vaccination to review any AEs and SAEs. Adverse events and serious adverse events will be collected through 7 days following vaccination.

Solicited **systemic AEs** will be collected for 7+ days post each vaccination and will include the following: fevers, headache, fatigue/malaise, nausea, body ache/myalgia, general activity level, and vomiting. Solicited **injection site AEs** will include the following: pain, tenderness, redness/erythema, and swelling/induration at injection site.

**Reporting of Deviations:** All deviations will be reported to the IRB at the time of annual continuing review. Note: if the deviation affects patient safety and/or risk, the event will be reported immediately.

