**Days 0-7: After the second vaccination:**

- The following data will be recorded on the memory aid form by the subjects each evening:
  - Oral temperature
  - Local reactions
  - General reactions
  - Concomitant medications given

**Days 1-3 and Days 8-10 after second vaccination:** Telephone and/or electronic communication

- An attempt of telephone and/or electronic communication will be made/sent between Days 1-3 and again on Days 8-10:
  - Appropriate data will be collected, and they will ensure the memory aid forms are being completed correctly
  - Any adverse events that have occurred will be collected
  - Questions the subject may have will be answered
  - Any concomitant medication will be recorded

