**Visit 3: 28-42 Days after Visit 2**

- Solicited AEs/unsolicited AEs will be reviewed and recorded in through 7 days following vaccination #2
- Targeted physical examination will be conducted if indicated.
- Any concomitant medication will be recorded.
- Any new immunizations since last visit will be reviewed and recorded.
- Approximately 20-40 mL of blood will be collected for HAI and MN assays to influenza virus antigens, phenotypic B, and T cell responses, B and T cell specific influenza responses, CBC d/p, quantitative CD4+/CD8+/CD19+ levels, and quantitative serum IgM and IgG concentrations.
- A second blood draw will be obtained post-IVIG/SCIG if administered.
- Only during influenza season, a nasal swab will be obtained, regardless of symptoms.
- For the 2019/2020 enrollment season, subjects who are not able to return for visit 3 will have an arrangement for a blood draw to be done locally and shipped to the research team. Subjects will also be called and asked about their health and medication changes. Also, they will be asked to collect a nose swab and mail it to the research team.

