## Methods and Timing for Assessing, Recording, and Analyzing Safety Parameters

### a. Adverse Events, Reactogenicity, Serious Adverse Events

The investigator is responsible for reporting:

- Any Grade 3 Adverse event that is not attributable to underlying disease for which the transplant was undertaken, **or** not attributable to GVHD, **or** not attributable to complications of immunosuppressive medications **and** are observed or reported through 7 days following vaccination, regardless of their relationship to study product.
- Any other AE will not be reported unless it meets the SAE criteria (see Section 16.f).

A physician, nurse, nurse practitioner, and/or physician's assistant will assess initial vaccine reactions for at least 15 minutes after vaccination. Subjects will be asked to record both solicited vaccine reactions

(reactogenicity) and any unsolicited AEs on a memory aid for 7+ days after each vaccination (Day 0 through Day 7). Study personnel will attempt to contact the subjects by telephone and/or electronic communication at 1 to 3 days and again 8-10 days after each vaccination to review any AEs and SAEs.

AEs and SAEs will be collected through 7 days following each vaccination. Adverse events will be followed until resolution or until considered stable. **Solicited injection site AEs** will include the following: pain, tenderness, erythema/redness, and swelling/induration (**Table 4**). **Solicited systemic AEs** will be collected for 7+ days post each vaccination and will include the following: fevers, fatigue/malaise, headache, nausea, body ache/myalgia, generally activity, and vomiting (**Table 5**).

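### Halting rules 4 and 6 are met by one qualifying case and have no time limit, but after dose 2 no scheduled AE question covers events that begin after the day 8-10 contact

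*Protocol*

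**What the plan says.** Protocol section 16.j lists seven halting rules. Rule 4 is met when "1 or more subjects have intramuscular injection-site ulceration, abscess, or necrosis" and rule 6 when "1 or more subjects have acute weakness of limbs or cranial nerve innervated muscles". Neither states a time limit, a grade, or a required relationship to vaccine. A lead-in clause removes events due to trauma or accident, scheduled hospitalization or surgery, disease relapse, GVHD, or infection arising from immunosuppression. Once a rule is met, enrollment and vaccination stop until the DSMB reviews the case and recommends proceeding.

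On collection, section 7 says: "Adverse events and serious adverse events will be collected through 7 days following vaccination". Section 16.a agrees: "AEs and SAEs will be collected through 7 days following each vaccination". Both sections limit investigator reporting to certain Grade 3 AEs through Day 7 and to events meeting the SAE criteria.

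After dose 2, section 14 provides at the day 8-10 contact that "Any adverse events that have occurred will be collected". An optional visit inside that window replaces the contact. For Visit 3, 28 to 42 days after dose 2, the text is "Solicited AEs/unsolicited AEs will be reviewed and recorded in through 7 days following vaccination #2". In Table 3 the row "Adverse event assessment" is marked at Visits 1 and 2, the telephone or electronic contacts and the optional visits. It is blank at Visit 3, in the influenza season, at Visit 4 and at June 30.

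**The concern.** A rule that one case can trigger works only if that case is found. Rules 4 and 6 run without limit, while the active search for AEs ends with the day 8-10 contact. After that, the protocol relies on someone volunteering the event or on staff noticing it.

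The reporting threshold adds a second mismatch. Rules 4 and 6 apply at any grade, yet a late event that is below Grade 3 and not an SAE need not be reported under sections 7 and 16.a. Weakness or an ulcer of that degree could meet a halting rule without meeting the reporting rule.

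If such an event is missed, other children continue to be vaccinated without the DSMB review that section 16.j requires. The high-dose product is not approved below age 65. The protocol itself lists severe limb weakness among the very rare side effects and excludes children with a history of Guillain-Barre syndrome.

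**Working it through.** The plan gives no event rate or operating characteristic for the halting rules, so there is no figure to reproduce. The check compares the rules with the contact schedule and then counts days.

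**1. Time limits in section 16.j**

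| Rule | Trigger | Time limit stated |
|---|---|---|
| 1 | one severe, vaccine-related SAE | 7 days |
| 2 | same related Grade 3 reactogenicity event in 4 subjects (8 in 2019-20) | none, but the memory aid covers Day 0 to 7 |
| 3 | related urticaria in 3 subjects | none |
| 4 | injection-site ulceration, abscess or necrosis in 1 subject | none |
| 5 | laryngospasm, bronchospasm or anaphylaxis in 1 subject | 24 hours |
| 6 | acute limb or cranial-nerve weakness in 1 subject | none |
| 7 | any death | 7 days |

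Rules 4 and 6 are the only single-case rules without a limit.

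**2. Scheduled contacts after dose 2 (section 14 and Table 3)**

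| Contact | Asks about new AEs? |
|---|---|
| Day 1-3 | yes |
| Optional visit, day 5-10 | marked in Table 3; volunteers only |
| Day 8-10 | yes |
| Visit 3, day 28-42 | only AEs through Day 7; also a medication review, and an examination if indicated |
| 2019/2020 call replacing Visit 3 | general health and medication changes; only subjects who cannot return |
| Weekly in influenza season | influenza-like illness |
| Visit 4, day 138-222 (180 − 42 to 180 + 42) | no AE item; optional in 2019-20 |
| To June 30 | proven influenza |

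After dose 1 the position is better: Table 3 marks an AE assessment at Visit 2. The Visit 2 text in section 14 lists no AE review, however, and the Day 7 wording makes no provision for recording a later onset there.

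**3. Days from the last AE question to Visit 3**

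Gap = Visit 3 day − contact day. Share = gap / Visit 3 day.

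| Last contact | Visit 3 | Gap | Share |
|---|---|---|---|
| day 10 | day 28 | 28 − 10 = 18 | 18/28 = 64.3% |
| day 8 | day 28 | 28 − 8 = 20 | 20/28 = 71.4% |
| day 10 | day 42 | 42 − 10 = 32 | 32/42 = 76.2% |
| day 8 | day 42 | 42 − 8 = 34 | 34/42 = 81.0% |

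Counted from the Day 7 cut-off, days 8 to 28 are 28 − 8 + 1 = 21 days and days 8 to 42 are 42 − 8 + 1 = 35 days. Because Visit 3 does not ask about later onsets, the interval without an AE question in fact continues. From a day 10 contact to Visit 4 it is 138 − 10 = 128 to 222 − 10 = 212 days.

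**The case against.** The strongest reply is that a rule without a time limit is broader than one with a limit, so the missing limit does no harm in itself. That is right. A window closing at Visit 3 could even narrow rules 4 and 6: a case learned of on day 60 would then no longer count.

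There are also several passive routes. Families are told to call about any concerning medical event. Section 13.e allows unscheduled visits to evaluate AEs, and section 16.b recognises AEs that surface at study visits or in clinical care. Subjects are recruited from the sites' own transplant clinics. Section 16.h requires notice of an SAE within 24 hours of site awareness, with no Day 7 limit stated, and the DSMB may meet ad hoc. Reactions that begin by Day 7 are followed to resolution or stability, so for rule 4 only lesions that first appear later are at issue. The attribution clause would remove some late abscesses and some late weakness in these patients. All of this stands, and it makes a missed event unlikely. None of it is a scheduled question about late onset, and the 24-hour route covers only events meeting the SAE criteria.

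A reader might infer that the halting rules lapse at Day 7, since AEs and SAEs are among the data listed for halting. Section 16.j also provides for notifying CBER whenever during the study a stopping rule is met, which points the other way. The text does not settle this, and the DSMB charter is not among the documents.

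A reader might also want a limit for rule 3 ("3 or more subjects have urticaria considered to be study vaccine-related"). It would add little: section 11.b describes hives as an immediate reaction, and the rule needs three related cases.

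**Conclusion.** The point holds as a gap in active ascertainment: two single-case halting rules without a time limit are paired with AE collection that ends at Day 7, and after dose 2 nothing scheduled asks about new AEs beyond day 10. A late event that is below Grade 3 and not an SAE also escapes the reporting rule.

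Two stronger readings should be resisted. A reader might infer that a late event could not reach the DSMB or halt the trial; sections 16.h and 16.j provide that route once the site knows. A reader might also take 64% to 81% as the share of qualifying events missed. It is a share of calendar days. The documents give no onset times for these events, so the number affected cannot be estimated. It is probably very small, because severe weakness is described as very rare and several passive routes exist. In 2019-20 the children still to be vaccinated are mainly repeaters from 2018-19, which limits exposure further.

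The conclusion assumes that the DSMB charter does not already require active follow-up for these events. The change is a cheap safety improvement that should be made; the documents do not show that any event has been or would be missed.

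**What to change.** Keep rules 4 and 6 free of a closing date, and say in section 16.j that they apply whenever the site learns of a qualifying event, subject to the existing attribution clause.

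At Visit 3, or the 2019/2020 call that replaces it, add one targeted question: any new limb or cranial-nerve weakness, or any injection-site ulceration, abscess or necrosis, since dose 2? Record and report a positive answer at any grade. Allow the same recording at Visit 2 for dose 1. Align sections 7 and 16.a, the Visit 2 and Visit 3 text in section 14, and Table 3. Leave rule 3 as it is.

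The cost is a protocol amendment submitted to the FDA and IRB and put into effect at nine sites, one question at a contact already scheduled, and possibly a few more events for the DSMB to review.
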